Study identification : NCT03741907

**Title : Comparing French Ambulatory and MISGAV-LADACH
C-Section Techniques**

Principal investigator : Professor [name]

[contact]

Location : Mongi Slim University Hospital , La Marsa , TUNISIA

Date of approval : 05.05.2018

STUDY PROTOCOL

This study is a randomized clinical trial conducted at Mongi Slim University Hospital, La Marsa, Tunisia; between August 2018 and January 2019.

The study was approved by the local hospital ethics committee (reference number 05/18) and was registered at clinicaltrials.gov (NCT03741907). Data collection was conducted in compliance with Tunisian laws regarding personal data protection.

During the study period, women with a singleton pregnancy and an elective CS indication were eligible. There were no restrictions regarding the number of previous CS, fetal presentation or fetal weight. Following subjects were not included in the sample: women under 37 weeks of gestation, women with a prenatally diagnosed fetal pathology (intrauterine growth restriction, malformation, genetics disorders), a morbidity adherent placenta, an adnexal mass or a myoma in the lower uterine segment.

All women who met the inclusion criteria were invited to participate in the study during their final prenatal visit. Those providing written informed consent were consecutively included in a preliminary patient list managed by an investigator not involved in patient care.

Before randomization, we excluded women who were initially recruited but who had to be operated either as an emergency before the originally scheduled date (example: in case of acute fetal compromise) or by a different surgeon than those assigned to the study (Figure

1). Women recruited into the study were given a study number on their delivery day, in a chronological order.

All participants were randomly assigned to either FAUCS or MLC group. Group allocation was predetermined by an investigator who was not involved in patients care and using the Kendall B.B Smith table ⁷.

The participants as well as, the residents involved in patient care, and the investigators were blinded to the cesarean technique before the operation and were informed at discharge. Both anesthetists and surgeons were informed of the cesarean technique on the due date in the operating room.

The MLC spinal anesthesia protocol included 500cc of isotonic crystalloid solution for vascular filling, bupivacaine 7 to 10 milligrams (depending on the patient's height), morphine 100 micrograms, and sufentanil 10 micrograms.

The FAUCS spinal anesthesia protocol included no vascular filling, no morphine, bupivacaine 7 to 10 mg (depending on the patient's height), and sufentanil 10 micrograms.

A bladder catheterization was performed on the MLC group by using a 16 or 18-F catheter prior to the skin incision. In both groups, a single dose of a first-generation cephalosporin was administered intravenously.

All FAUCS surgeries were performed by two senior surgeons ([name] and [name]). Both were experienced with the paravesical approach and had performed more than 30 cases previously. The MLC cesarean operations were performed by same seniors or residents who performed vast majority of the operations in the unit.

For this study, we performed the MLC technique as described in 1999 ³.Regarding the FAUCS approach described in 2017, the use of skin glue for closure is recommended ⁶. In order to

ensure that all the patients were virtually indistinguishable, we alternatively employed a subcuticular absorbable Vicryl suture for the skin closure.

Hematocrit levels were assessed before and after surgery. Analgesics were administered by the nursing staff, upon patient's requests and visual analogue scale (VAS)⁸. Assessments with VAS were made every 6 hours: H0,H6,H12,H18, and H24. A standardized analgesics scheme was used:

First intention: 100 mg Ketoprofen intra-rectal route every 6 hours.

Second intention: intra venous1g paracetamol every 6 hours.

Third intention: tramadol 50 mg oral route every 6 hours.

A first standing was proposed to all women everyhour during the first post operative day.

The bladder catheter was removed as soon as the woman was able to walk alone.Normal oral food intake was initiated as soon as gas passage occurred and the patient felt hungry.

Women were evaluated by the end of the first day. If there were no complications and if the patient felt autonomous and pain-free, they were discharged 24 hours after the surgery. In the other cases, patients were discharged at least 48 hours after surgery after a similar evaluation of maternal autonomy.

The primary outcome measure of the study was the post-operative mean pain score (PMPS).

PPMS = (VAS H0+ VAS H6 + VAS H12+ VAS H18 + VAS H24)/5.

Secondary Outcome Measures were:

- VAS max : defined as the highest post operative pain score felt during the first day.
- Total dose of administrated analgesics during the first 24 hours (mg).

- Calculated estimation of blood loss (cEBL): derived by multiplying the calculated maternal blood volume by the percent of blood volume lost, were the maternal blood volume was calculated by Nadler's formula based on the patient's weight, and height. The percent of blood volume lost was calculated with Brecher's formula⁹ [$\{(\text{predelivery hematocrit (HCT)} - \text{post delivery HCT})/\text{predelivery HCT}\}$].
- Surgery time in minutes: T1: Delay between skin incision and hysterotomy; T2: Delay between hysterotomy and fetal extraction (min); T3: time spent for uterine sutures; T4: total duration of the surgery.
- Rate of short-term incidents: hemorrhage, transfusion, bladder injury or any other complication.
- Maternal autonomy: time to first spontaneous urination, time to first standing; time to first complete meal.
- Newborn overall condition: Neonatal acid base balance (Cord blood gases, pH and eucapnic pH¹⁰; Apgar score at 1 and 5 minutes after birth, rate of neonate hospitalization.
- Delay to hospital discharge (days).

Statistics

The sample size (N) calculations were based on the post-operative mean pain score (PMPS) as the main outcome measure. The mean (m_1) and standard deviation (σ) for the PMPS in the MLC group were estimated by reviewing the records of 80 consecutive women who underwent this procedure in 2017. These values were approximately $m_1=3.8$; $\sigma=2$. We aimed to detect a decrease of 60% in the PMPS in the FAUCS group (m_2), taking into account the level of significance ($p=.05$) and the expected power of the study (80%), with $\alpha=0.05$ and $\beta=0.10$; we used the following formula: $N = M / D_s^2 \cdot M = 2 * (z_{1-\alpha} + z_{1-\beta}) = 17.1$; $D_s = (m_1 - m_2) / \sigma$; $N = 17.1 / (0.6 m_1 / \sigma)^2$. 45 patients per group were required to detect a

decrease of 60% in PMPS scores between the two groups. Ultimately, we recruited 50 participants for each group to account for possible losses.

We measured 44 outcome variables. The metrics were grouped into four categories: surgery, overall morbidity, neonatal outcomes and maternal autonomy during recovery. All the analyses were conducted in RStudio (version 3.5.1). We performed unequal variance t-tests for all continuous variables and evaluated each distribution for normality using the Shapiro Wilk test. Continuous variables were analyzed with the student's t test and Mann-Whitney test. We performed asymptotic generalized Pearson's chi-squared tests for the categorical variables. When the categorical variables were ordinal, we used the Cochran-Armitage test, comparing one ordinal variable with a dichotomous one. All tests were performed as 2-tailed tests, and $p < .05$ was accepted as statistically significant.

To visualize the results, we employed smoothed kernel density plots of continuous outcome variables for FAUCS compared with the MLC values, which were viewed on a log scale where applicable.

5. S BD, J C. Extraperitoneal versus transperitoneal cesarean section in surgical morbidity in a tertiary care centre. *Int J ReprodContraceptObstet Gynecol.* 2017 Jul 26;6(8):3397–9.

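### The number of previous caesareans is unrestricted at entry but unused in the analysis, which gives up some precision for T1, T4 and blood loss

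*Combined protocol and SAP*

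**What the plan says.** The eligibility paragraph of the Study Protocol section admits women with a singleton pregnancy and an elective indication, and adds: "There were no restrictions regarding the number of previous CS, fetal presentation or fetal weight".

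On allocation, the same section says: "Group allocation was predetermined by an investigator who was not involved in patients care and using the Kendall B.B Smith table". Numbers were issued in sequence: "Women recruited into the study were given a study number on their delivery day, in a chronological order". It mentions no strata, blocks or minimisation.

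The Statistics section describes these comparisons:

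- Continuous variables: "We performed unequal variance t-tests for all continuous variables and evaluated each distribution for normality using the Shapiro Wilk test", followed by "Continuous variables were analyzed with the student's t test and Mann-Whitney test".
- Categorical variables: "We performed asymptotic generalized Pearson's chi-squared tests for the categorical variables".
- Ordinal variables: "we used the Cochran-Armitage test, comparing one ordinal variable with a dichotomous one".

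None of these carries a covariate or a stratum. After the eligibility paragraph, the number of previous caesareans does not appear again. T1, T4 and cEBL are secondary outcomes. The primary outcome is the post-operative mean pain score (PMPS).

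**The concern.** First caesareans are pooled with repeat operations of any order. T1 is the interval in which the surgeon would meet scarring from an earlier operation at the same site, so previous caesarean could plausibly affect T1 and, through it, T4 and blood loss. The protocol excludes adherent placenta, adnexal masses and lower-segment myomas, yet neither restricts nor models previous surgery.

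A factor that predicts the outcome and is ignored has two consequences. Its share of the between-woman variance stays in the error term, so the interval is wider than it need be. And if the arms differ on it by chance, the unadjusted difference in that trial is shifted and the planned tests cannot remove the shift. One imbalance could also move T1, T4 and cEBL together and look like several findings in agreement.

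**Working it through.** The plan gives no figure of its own on this point: no share of women with a previous caesarean, no SD for T1, T4 or cEBL, and no association with previous caesarean. The check therefore takes 50 per arm from the Statistics section and uses labelled assumptions for the rest.

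**1. Chance imbalance.** Assume a share p of women have a previous caesarean, with unstratified allocation. The counts in the two arms are then independent Binomial(50, p). Exact enumeration gives:

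| p (assumed) | arms differ by 10 points or more | by 20 points or more |
|---|---|---|
| 0.1 | 13% | 0.2% |
| 0.3 | 33% | 3.8% |
| 0.5 | 37% | 5.7% |
| 0.6 | 36% | 5.2% |

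**2. What a 10-point gap does to the outcome.** If a yes/no factor explains a share R² of the variance, its effect is √(R²/(p(1−p))) outcome SDs, and a 10-point gap shifts the arm difference by 0.10 times that. For p = 0.5 and R² = 0.10 this is 0.10 × √(0.10/0.25) = 0.06 SD. For p = 0.3 and R² = 0.30 it is 0.10 × √(0.30/0.21) = 0.12 SD. The unadjusted standard error is √(2/50) = 0.20 SD, so the shift is about 0.3 to 0.6 of one standard error.

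**3. Precision gained by adjustment.** Before any cost, the standard error is multiplied by √(1−R²). Two extra terms with 100 women cost about 2% of variance through chance association with arm (98/96 = 1.021). If R² is read as a sample value, losing two residual degrees of freedom costs a similar 2%. Charging both multiplies the standard error by about 1.021.

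| R² (assumed) | √(1−R²) | cut in SE | after both costs | net cut |
|---|---|---|---|---|
| 0.05 | 0.975 | 2.5% | 0.995 | 0.5% |
| 0.10 | 0.949 | 5% | 0.968 | 3% |
| 0.20 | 0.894 | 11% | 0.913 | 9% |
| 0.30 | 0.837 | 16% | 0.854 | 15% |

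Before these costs, 1/(1−R²) for R² = 0.10 to 0.30 is 1.11 to 1.43, equivalent to 11% to 43% more women. The difference detectable with 80% power at 50 per arm falls from 0.560 SD to between 0.532 SD (R² = 0.10) and 0.469 SD (R² = 0.30).

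**4. The primary outcome.** The Statistics section assumes a PMPS mean of 3.8, an SD of 2 and a 60% fall, so the difference is 0.6 × 3.8 = 2.28. At 50 per arm this is (2.28/2)/0.20 = 5.7 standard errors. Two-sided power at 0.05 is Φ(5.7 − 1.96), above 99.9%. On the plan's own inputs, PMPS does not need the extra precision.

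**The case against.** The strongest reply is that nothing here is an error. Under proper randomisation the unadjusted tests are unbiased and keep their type I error, and chance imbalance in previous caesarean is already part of the unadjusted standard error. Error-term noise and chance imbalance are then largely one variance component described twice. This stands, and it limits the point to efficiency.

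A reader might infer three stronger things, none of which the documents support:

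- That previous caesarean is a main source of variation in operating time and blood loss. No figure in the documents shows this. The mechanism is plausible, but at R² near 0.05 the gain nearly vanishes.
- That every interval is widened and the primary result is at risk. Nothing ties previous caesarean to all 44 outcome variables, and PMPS power exceeds 99.9% on the plan's own inputs.
- That allocation was certainly unstratified, or was faulty for that reason. The protocol is short and silent on strata, and a simple random list is a legitimate method.

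Two practical objections also stand. The text reports recruitment as done, so separate lists are no longer useful if allocation is complete, and a model adopted after outcome data were seen is post hoc. The Statistics section also foresees non-normal data, so an untransformed linear model may not suit a skewed time.

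Finally, adjustment cannot address other differences between the arms, such as who operated and the fluid given before spinal anaesthesia. That is a limit on what this change achieves and does not count against making it.

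**Conclusion.** The point holds as a low-cost improvement to the analysis of T1, T4 and cEBL. The eligibility rule and the list of unadjusted tests are explicit; the absence of stratification is read from silence. What is lost is precision and the ability to correct a chance imbalance that, for p between 0.3 and 0.6, reaches 10 points in about a third of trials.

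The size rests entirely on an assumed R². At 0.10 to 0.30 the standard error would fall by about 5% to 16%, or about 3% to 15% net of the extra terms. At about 0.05 or less there is almost nothing to gain. The unadjusted results remain valid, and the primary pain comparison does not depend on this change.

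**What to change.** Keep the broad eligibility. In the Statistics section:

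1. For T1, T4 and cEBL, fit a linear model of outcome on arm plus number of previous caesareans (0, 1, 2 or more). Use the log scale for T1 or T4 where skewed, and report the arm effect there as a ratio. Give the adjusted arm difference with its 95% CI, and keep the unadjusted test alongside.
2. If the model is added after outcome data were seen, label it a supporting analysis.
3. Leave the PMPS primary analysis unchanged. An adjusted PMPS model may be shown as a sensitivity analysis only.
4. Show the number of previous caesareans by arm in the baseline table.
5. State whether allocation was stratified. If allocation is complete, do not pursue separate lists.

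The cost is two model terms per outcome, one variable from the obstetric history and a few lines of text. No extra women or procedures are needed.

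### Does telling women their arm at 24-hour discharge compromise the H24 pain score in the primary outcome?

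*Combined protocol and SAP*

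**What the plan says.** All of this is in the study protocol text of the combined document. Participants, "the residents involved in patient care, and the investigators were blinded to the cesarean technique before the operation and were informed at discharge". On pain scoring: "Assessments with VAS were made every 6 hours: H0,H6,H12,H18, and H24". The primary outcome is their plain mean: "PPMS = (VAS H0+ VAS H6 + VAS H12+ VAS H18 + VAS H24)/5".

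On discharge, women are evaluated by the end of day one. Where there are no complications, "if the patient felt autonomous and pain-free, they were discharged 24 hours after the surgery". Everyone else stays for 48 hours or longer and is assessed again before leaving. Time to discharge is a secondary outcome, counted in days.

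Two further details bear on masking. The skin was sutured rather than glued in the FAUCS arm to "ensure that all the patients were virtually indistinguishable". In the other direction, "A bladder catheterization was performed on the MLC group by using a 16 or 18-F catheter prior to the skin incision", and the catheter stayed in until the woman could walk unaided. The Statistics section plans no analysis without H24 and no check of blinding.

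**The concern.** PMPS is a self-reported score, so knowing the arm could colour it. The matched skin closure suggests that masking was meant to outlast the operation, and disclosure is tied to discharge. For women who leave at 24 hours, discharge and the last reading share one nominal time, and nothing says the score is taken first. Discharge delay in days cannot show the order.

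Early discharge depends on feeling pain-free, so the share of women affected could differ by arm. If some H24 scores were given after disclosure, the primary outcome would mix masked and unmasked ratings in different proportions in the two arms, and nothing in the analysis would show it.

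**Working it through.** **Order of events.** The protocol's sequence is: evaluation by the end of the first day; a finding that the woman is free of complications, autonomous and pain-free; discharge; disclosure at discharge. A judgement about pain therefore comes before disclosure. The text does not say that this judgement is the H24 score. But for H24 to follow disclosure, staff would have to take the last scheduled reading after deciding on discharge and revealing the arm. Women who stay 48 hours or longer are unaffected at H24.

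**Inputs.** From the Statistics section: control mean 3.8, SD 2, a 60% decrease, 50 per group, two-sided 0.05. From the PMPS formula: H24 has weight 1/5. Assumed, because the documents give neither: q, the share of women scoring H24 after disclosure, and d, the resulting shift in H24 between arms, in points. The planned difference is 0.6 × 3.8 = 2.28. (The plan's 45 per group does not follow from its printed formula, 17.1/(2.28/2)² = 13.2. That is a separate matter and nothing below uses it.)

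**Shift in PMPS** = d × q / 5.

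**False-positive rate.** The standard error is 2 × √(2/50) = 0.40. With t(0.975, 98 df) = 1.984, the smallest significant difference is 1.984 × 0.40 = 0.79. Two-sided rejection probabilities under no true effect, from the noncentral t with 98 df:

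| d | q | PMPS shift | Share of 2.28 | P(p < .05) |
|---|---|---|---|---|
| 1 | 0.5 | 0.10 | 4.4% | 5.7% |
| 2 | 0.5 | 0.20 | 8.8% | 7.9% |
| 2 | 1 | 0.40 | 17.5% | 16.8% |

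If the shares differ, say 80% of FAUCS and 30% of MLC women with opposite shifts of 1 point each, the bias is (0.8 + 0.3) × 1/5 = 0.22.

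**How far the last row can be believed.** It needs all 100 women to be discharged pain-free at 24 hours, all to be scored after disclosure, and a 2-point shift between arms among women who have just said that they feel pain-free. The protocol gives no VAS threshold for pain-free, but such women have little room to score lower. For H24 alone to create the smallest significant difference, disclosure would have to separate the arms by 5 × 0.79 = 3.97 points at H24 on average; to create 2.28 it would take 5 × 2.28 = 11.4 points.

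**Would an analysis without H24 help?** The obvious candidate is the mean of H0 to H18 in all women, with the result called not robust if the two versions disagree on p < .05. Precision is no obstacle. With an equal correlation r between readings, the four-reading SD is √[20/(1+4r) × (1+3r)/4], which is 2.08, 2.04 and 2.02 for r = 0.3, 0.5 and 0.7. The smallest significant difference becomes 0.82, 0.81 and 0.80.

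The obstacle is what a disagreement would mean. In simulated trials with no disclosure effect (50 per group, five-reading SD 2, r from 0.3 to 0.7), the versions disagree in about 3% to 9% of trials at true differences of 0.8 to 1.2, the region where a 0.40 bias could matter (0.79 to 0.79 + 0.40 = 1.19). At 2.28 they essentially never disagree. A real treatment difference at 24 hours would also produce disagreement.

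**Other cues to the arm.** Besides the catheter, vascular filling is described for MLC only, and residents could operate in MLC but not in FAUCS, although residents in patient care are listed as blinded. Any of these could reveal the arm from H0 and touch all five readings. The H0 to H18 mean would then be no better masked than PMPS, and agreement between the two would reassure falsely.

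**The case for a change.** The best case for a change is that the gap is real and the remedy nearly free. The order of H24 and disclosure is not stated, the outcome is subjective, the sponsor altered the skin closure to protect masking, and the four-reading mean needs no new data. Applying it to every woman avoids selecting on being pain-free, which dropping H24 only for early discharges would do.

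The factual part stands. The shared nominal time, the 1/5 weight, the missing order and the absence of any such analysis are all as described. It is also true that the protocol does not say who collected the VAS or whether they were masked, and its wording claims blinding only up to the operation.

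The inference does not follow. A shared rounded hour is not evidence that scoring came second, and the evaluation before discharge points the other way. The remedy cannot tell disclosure from chance or from a late treatment effect, and it leaves the cues present from H0 untouched. The order is better settled from the recorded times, and discharge delay in days should help to identify the women discharged at 24 hours and so cap q in each arm.

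**Conclusion.** No change to the plan is needed. This is a gap in documentation that the authors can close when they report: whether H24 preceded disclosure, who was masked from H0 to H24, and who collected the scores. If masking cannot be documented, PMPS should be described as not reliably blinded. That is a limitation to state, and re-analysis would not repair it.

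Under the assumed shifts, the H24 effect is 0.10 to 0.20 PMPS points when half the women are affected (false-positive rate 5.7% to 7.9%), with an implausible extreme of 0.40 (16.8%). None of these would overturn the planned 2.28. The figures rest on SD 2, 50 per group and assumed d and q; the documents show neither unblinding nor the direction of any bias. The mean of H0 to H18 may be shown descriptively with its interval, but a rule that reads disagreement on p < .05 as an effect of disclosure would mislead more than it would inform.

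### Who may operate depends on the arm (FAUCS: two seniors; MLC: the same seniors or residents, split not given), so differences in surgical times, blood loss and incidents may mix technique with operator grade

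*Combined protocol and SAP*

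**What the plan says.** The Study protocol section, where it describes the operators, says "All FAUCS surgeries were performed by two senior surgeons", each with more than 30 earlier cases by that approach. For the comparator it says "The MLC cesarean operations were performed by same seniors or residents who performed vast majority of the operations in the unit". It gives no count or share for either grade within MLC, and no rule for choosing between a senior and a resident.

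The nearest safeguard is the exclusion, before randomization, of women who had to be operated on "by a different surgeon than those assigned to the study". Allocation came from a random number table, with no stratification by operator described. Surgeons learned the technique in the operating room on the day.

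The secondary outcomes include four surgical times (T1 to T4), calculated blood loss (cEBL) and "Rate of short-term incidents: hemorrhage, transfusion, bladder injury or any other complication". For continuous variables the Statistics section says "We performed unequal variance t-tests for all continuous variables" and also names the "t test and Mann-Whitney test"; categorical variables get chi-squared or Cochran-Armitage tests. No covariate, operator term or operator-restricted analysis appears. The title presents the aim as "Comparing French Ambulatory and MISGAV-LADACH" cesarean techniques.

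**The concern.** Randomization balances patients between arms. It cannot balance a factor that the assigned arm itself determines. Here a resident could be the operator only if the woman was allocated to MLC, so any difference in grade follows from allocation and is not a chance imbalance.

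Surgical times, blood loss and complications such as bladder injury arise directly from the operation and can depend on who performs it. If residents did a sizeable share of MLC and their results differ from the seniors', the unadjusted tests would credit that difference to technique. The stated question is about technique, and the documents do not define the comparison as one between packages of care that include the operator.

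**Working it through.** **What the safeguards do.** The surgeon exclusion limits operators to those assigned to the study. Residents are among the MLC operators, so it does not equalise grade between arms. No other safeguard is described.

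**Form of the bias.** Let q be the share of MLC cases done by residents, and d the effect of a resident rather than a senior operating in those cases, in within-grade SD units. FAUCS has no resident cases. With equal techniques, the expected MLC-minus-FAUCS difference is b = q × d. The plan has no figure of its own to reproduce on this point.

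**Inputs.** From the documents: 50 per arm ("Ultimately, we recruited 50 participants for each group"), two-sided 5% tests, unadjusted two-group comparison. Assumed: q, d, approximate normality and equal within-grade SDs.

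**False-positive rate for technique.** The MLC variance is 1 + q(1 − q)d². The standard error is SE = √(1/50 + MLC variance/50). The rejection rate comes from the noncentral t with Welch degrees of freedom (about 98) and noncentrality b/SE.

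One case in full, q = 0.5 and d = 0.5: b = 0.25; variance = 1 + 0.25 × 0.25 = 1.0625; SE = √(2.0625/50) = 0.2031; b/SE = 1.23; rejection rate 23%.

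| q | b (d = 0.2) | Rate (d = 0.2) | b (d = 0.5) | Rate (d = 0.5) |
|---|---|---|---|---|
| 0.1 | 0.02 | 5.1% | 0.05 | 5.7% |
| 0.25 | 0.05 | 5.7% | 0.125 | 9.4% |
| 0.5 | 0.10 | 7.8% | 0.25 | 23.0% |
| 0.9 | 0.18 | 14.5% | 0.45 | 60.1% |

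At q = 0 the rate is the nominal 5%. Reversing the sign of d leaves the rates unchanged and reverses the direction of the difference. For the Mann-Whitney test, simulation of 40,000 trials per setting at d = 0.5 gave about 6%, 9%, 22% and 58%.

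**Thresholds that do not depend on a chosen d.** With SE = √(2/50) = 0.2 and 98 degrees of freedom, the rejection rate reaches 10% at |b| = 0.13 SD, 20% at 0.23 SD and 50% at 0.40 SD. Below about 0.13 SD the problem is minor.

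**Precision of a senior-only comparison.** The SE relative to the full sample is √(1/50 + 1/(50(1 − q))) / √(2/50).

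| q | Senior MLC cases | SE ratio |
|---|---|---|
| 0.25 | 37.5 | 1.08 |
| 0.5 | 25 | 1.22 |
| 0.9 | 5 | 2.35 |

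No rate is computed for incidents, because the documents give no expected frequency.

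**The case against.** The operator rule is disclosed, not hidden, and the document is a short protocol rather than a results report. It mentions 44 outcome variables without itemising them all, so operator may have been recorded. This stands: what can be said is that the MLC split is not given and that no use of operator in the analysis is described.

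The description of the MLC operators suggests that they were familiar with the unit's routine surgery, so d could be small. Also, since women facing a non-study surgeon were excluded beforehand and the technique was disclosed only in the operating room, a senior able to do FAUCS was presumably available for every randomized woman. Both are inferences that bear on the size of the bias. Neither shows who operated, and neither removes the asymmetry.

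Three stronger readings are tempting, and the documents support none of them:

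- **That the surgical outcomes are in fact confounded, or that the confounding favours FAUCS.** If seniors did all the MLC cases, the bias is zero. No outcome data by grade are given, so the direction is open.
- **That confounding is only partial because the seniors also did MLC cases.** The text names a pool of permitted operators without counts. The resident share could lie anywhere from none to nearly all.
- **That the primary pain result is biased by operator grade.** Nothing in the documents quantifies this, and it is not claimed here.

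**Conclusion.** The point holds for the secondary surgical outcomes. The permitted operators differ by arm, nothing described balances or adjusts for this, and the planned tests cannot separate technique from operator grade. Confidence is high about the asymmetry; the size of its effect is unknown.

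Under the assumptions shown, the consequence runs from negligible (about 5% to 14% false positives at d = 0.2 SD) to serious (6% to 60% at d = 0.5 SD) as q goes from 0.1 to 0.9. These figures are illustrations for a roughly normal continuous outcome, not estimates for this trial. The point warrants action because the remedy is cheap and changes what may be concluded about technique.

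**What to change.** The trial is described as already carried out, so the remedy is reporting and wording.

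1. Report the number of cases by operator grade in each arm, if operator identity can be retrieved. The cost is the retrieval and one table row.
2. Describe the full surgical comparison as senior-delivered FAUCS versus MLC by seniors or residents. Do not attribute its differences to technique alone unless step 1 shows that residents did few or no MLC cases. This is a wording change, and it applies even if operator identity is lost.
3. Only if enough senior MLC cases exist, add a clearly exploratory senior-only comparison of T1 to T4 and cEBL, adjusted for number of previous cesareans if recorded. Describe incidents without a test.

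State the downsides of step 3 beside its results. The senior MLC subset is not randomized and may contain harder cases, since eligibility set no limit on previous cesareans, presentation or fetal weight. Precision falls as tabulated, before any cost of adjustment, and at q near 0.9 the comparison is uninformative. For cEBL the arms also differ in vascular filling (500cc in MLC, none in FAUCS). Matching operators does not remove that difference, so the caution on attributing cEBL to surgical technique remains whatever step 1 shows.

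### Calculated blood loss (cEBL) has no fluid term, only the MLC arm receives 500 cc of filling, and haematocrit times are not fixed, so retained fluid can be counted as MLC blood loss

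*Combined protocol and SAP*

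**What the plan says.** The study protocol sets different fluid for the two arms: "The MLC spinal anesthesia protocol included 500cc of isotonic crystalloid solution for vascular filling", whereas "The FAUCS spinal anesthesia protocol included no vascular filling, no morphine". Further on in the same text, the only statement on haematocrit timing is "Hematocrit levels were assessed before and after surgery". It gives no clock time, and no order relative to the filling. Pain, in the same paragraph, has a fixed schedule: "Assessments with VAS were made every 6 hours: H0,H6,H12,H18, and H24".

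Under Secondary Outcome Measures, cEBL is "derived by multiplying the calculated maternal blood volume by the percent of blood volume lost". The blood volume comes from Nadler's formula, "based on the patient's weight, and height", and the percentage lost is the haematocrit fall divided by the predelivery haematocrit.

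The Statistics section compares continuous outcomes directly between arms, two-tailed at p < .05. It contains no adjustment for dilution, no sampling window and no record of fluids given. No directly measured blood loss is listed, although hemorrhage and transfusion appear separately among the short-term incidents.

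**The concern.** The cEBL formula treats the whole haematocrit fall as bleeding. Haematocrit also falls when fluid is added to the circulation, and here the filling differs by arm by design. The blood volume term does not correct for this, because it is computed from body size.

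A difference in cEBL between the arms could thus be reported as a difference in bleeding when part or all of it is dilution. Randomisation does not balance the error, since the fluid is tied to the arm, and more patients do not average it out. If the fluid is retained at the second sample, the error favours FAUCS. Because neither sampling time is stated, a reader cannot tell whether the error is present, in which direction, or how large it is.

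**Working it through.** The plan states no expected mean, SD or difference for cEBL, so it has no figure to reproduce. The check applies the plan's own formula.

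**Inputs from the documents**
- cEBL = BV × (HCTpre − HCTpost) / HCTpre (Secondary Outcome Measures).
- Filling: 500 cc in MLC, none in FAUCS (study protocol, spinal anesthesia).
- 50 women per arm, two-sided 0.05 (Statistics).

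**Assumptions, not in the documents**
- Blood volume BV = 5000 mL.
- True loss L = 500 to 800 mL, equal in both arms, with circulating volume otherwise restored, so that haematocrit falls by the fraction L/BV.
- Retained filling v = 0 to 500 mL in MLC, with no other fluid difference between the arms.

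**Case 1: first sample before the filling, v mL still circulating at the second**

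FAUCS: HCTpost = HCTpre × (1 − L/BV), so cEBL = L.

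MLC: HCTpost = HCTpre × (1 − L/BV) × BV/(BV + v), so cEBL = BV − (BV − L) × BV/(BV + v).

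False MLC excess = (BV − L) × v/(BV + v).

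Example with v = 125: 4500 × 125/5125 = 110 mL for L = 500, and 4200 × 125/5125 = 102 mL for L = 800.

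| Retained v (mL) | L = 0 | L = 500 | L = 800 |
|---|---|---|---|
| 0 | 0 | 0 | 0 |
| 50 | 50 | 45 | 42 |
| 125 | 122 | 110 | 102 |
| 250 | 238 | 214 | 200 |
| 500 | 455 | 409 | 382 |

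The L = 0 column is for comparison only. A real loss scales the error by (BV − L)/BV, which is 0.90 to 0.84 here.

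**Case 2: first sample after the filling, fluid gone by the second**

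HCTpre is lowered by the factor BV/(BV + v) and HCTpost is not diluted. The error in MLC is −v × (BV − L)/BV. For v = 125 this is −125 × 0.90 = −113 mL to −125 × 0.84 = −105 mL. For v = 250 it is −225 to −210 mL. With no bleeding it is simply −v.

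**What this could do to the test**

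With 50 per arm, the standard error of the difference is SD × √(2/50). For an assumed SD of 350 mL it is 70 mL. With no true difference and L = 500 to 800, the normal approximation gives a chance of p < .05 of about 9-10% at v = 50 and 31-35% at v = 125, against a nominal 5%. For assumed SDs of 250 and 450 mL, the v = 125 figures are about 54-59% and 21-23%.

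**The case against.** The strongest reply is that the bias may not exist. If the second sample was late enough for the crystalloid to have left the circulation and the first preceded the filling, the error is zero. This stands, and it limits the claim to what can happen under the plan as written. A reader might infer that cEBL is biased against MLC as a matter of fact. The documents do not support that, because the unstated times decide both whether there is an error and its sign.

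Three further limits also stand.
- The largest figures need all 500 cc to be circulating at the second sample, and 455 mL also needs a woman who lost no blood. Nothing in the documents supports either.
- The protocol describes only the filling that belongs to the spinal. Other perioperative fluids are not described for either arm, so the total fluid difference is not known to be 500 cc.
- A reader might infer from the discharge rule ("they were discharged 24 hours after the surgery. In the other cases, patients were discharged at least 48 hours after surgery") that women leaving early were sampled earlier. Nothing links the second sample to discharge, so this remains conjecture and is no part of the point.

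It can also be said that fluid belongs to the package being compared. That is true of any real effect of fluid on bleeding. Dilution of the marker is not bleeding, and the outcome is named blood loss. Hemorrhage and transfusion rates are listed as well, so cEBL is not the only bleeding outcome, but they do not measure the volume that cEBL claims to estimate.

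**Conclusion.** The point holds as a weakness in how a secondary outcome is measured. A formula without a fluid term is applied to arms that differ in filling, at sampling times that the plan leaves open. This can produce an apparent difference in blood loss with no difference in bleeding.

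The size runs from nothing, if the fluid has cleared, to 382-409 mL in the extreme case of full retention, with 102-110 mL if a quarter of the filling remains. The sign reverses if the first sample follows the filling. These figures rest on the assumed 5 L blood volume, the 500-800 mL true loss, and the spinal filling being the only fluid difference. The omission of sampling times is certain. The presence, direction and size of a bias in this trial's results are not. The primary pain score, its sample size and its analysis are untouched.

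**What to change.** **Measurement, in both arms**
- Draw the first haematocrit before any IV fluid is started.
- Draw the second at H24, before discharge. Under the discharge rule every woman is still in hospital then, and she already has a pain assessment.
- Record all IV fluid given between the two samples, and report it by arm.

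**Analysis**
- In all randomised women, report the cEBL difference with the MLC haematocrit corrected for retained volumes from 0 to 500 mL. Do this in both directions: multiply HCTpost by (BV + v)/BV for dilution at the second sample, and HCTpre by the same factor for dilution at the first.
- State the volume at which the difference disappears.

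**If samples were already taken**, as the protocol's past tense suggests, report the actual sampling times and fluids by arm with the same sensitivity analysis. Do not exclude women by sampling time: that selects after randomisation and may relate to arm or recovery. Word any conclusion on blood loss according to how much retained fluid would explain it, rather than requiring it to survive the full 500 mL.

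The cost is a sentence on sampling times, one recorded volume and one table. No extra sample or visit is needed, and treatment does not change. The downside is a slightly more cautious conclusion on cEBL.
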